### 11.2 Proper Standard of Care (SOC) Management Principles

Management principles are similar despite different etiologies. Oxygenation must be maintained, and the underlying cause of acute lung injury corrected. Meticulous attention is necessary to prevent nutritional depletion, O2 toxicity, superinfection, barotrauma, and renal failure, which may be worsened by intravascular volume depletion. While the diagnosis is being considered, life-threatening hypoxemia must be treated with a high FiO2 and monitored with repeated arterial blood gases or noninvasive oximetry. Prompt endotracheal intubation with mechanical ventilation and PEEP may be needed to deliver O2 if hypoxemia is refractory to O2 inhalation by face mask or nasal cannula. Despite the presence of alveolar edema, IV fluids should be given if needed to restore peripheral perfusion, urine output, and BP. Monitoring vascular volume is crucial because both hypovolemia and overhydration are deleterious. Physical findings and central venous pressure may be misleading in critically ill patients undergoing mechanical ventilation, and if severe hypoxemia persists, if skin perfusion is poor, if mentation is impaired, or if urinary output decreases (< 0.5 mL/kg/h), a reliable index of intravascular volume is needed immediately.

ECMO is a lifesaving modality that may be used when mechanical ventilation is unable to support life. However, the availability of ECMO is limited and decisions to allocate ECMO resources to patients are likely to be based on broader triage concerns. Therefore, ECMO is not considered part of SOC for the purposes of this study and the decision to escalate care to ECMO will be considered a treatment failure for the purpose of this study on the grounds that it signifies a determination that the lung is unable to support life even with mechanical ventilation.

### 11.3 Placebo

A normal saline placebo will be supplied by the hospital pharmacy in a labeled container indistinguishable from active drug.

## 11.4 Dosing Regimen

The escalating dosing regimen for RLF-100 is shown in Figure 2. Each infusion is planned for 12 hours duration, however, the infusion (either drug or placebo) may be slowed by up to 50% (for an 18-hour total infusion time) at the discretion of the site personnel if side effects cannot be managed to a clinically-acceptable level by the institution's ICU protocol or SOC. Monitoring of vital signs and other safety measurements will be ongoing and decisions relating to dose-reduction or cessation will be based on the evaluation of these parameters.

## 11.5 Potential Side Effects of Drug Therapy

Signs and symptoms to look for: facial flushing, tachycardia, hypotension, diarrhea. These will be monitored for the duration of the infusion, and for 12 h afterward, by blood pressure and heart telemetry measurements and patient observation. One identified side-effect of Aviptadil infusion is watery diarrhea. As noted above, non-bloody watery diarrhea  $> 3x/day$  requiring additional fluids and electrolyte supplementation is an enrollment exclusion. If watery diarrhea is observed during infusion, the infusion rate should be first reduced by 50% to relieve symptoms. If symptoms persist cease IV infusion.

# 12. ASSESSMENT OF SAFETY

## 12.1 Serious Adverse Events

Measurement of serious adverse events (SAE) will be the basis for assessing safety of RLF-100. All SAE's will be recorded on an IRB approved SAE Report Form. The SAE Report Form will include the exact nature of the event and the circumstances of the subject at the time of the event, in addition to the usual information required to document AEs or SAEs. Data on all the above will be collected on separate eCRF pages. The latest version of the AE dictionary, MedDRA, will be used for the classification and analysis of AEs entered in the study database. For regulatory reporting, SAEs will be coded using MedDRA.

## 12.2 Definition of Adverse Events

An adverse event (AE) is any untoward medical occurrence in a clinical study subject administered a medicinal (investigational or non-investigational) product. An AE does not necessarily have a causal relationship with the treatment. An AE can therefore be any unfavorable and unintended sign (including an abnormal finding), symptom, or disease temporally associated with the use of a medicinal (investigational or non-investigational) product, whether or not related to that medicinal (investigational or non-investigational) product. (Definition per ICH). AEs will be classified as drug-related, possibly drug-related, or non-drug related by the study safety monitor.

## 12.3 Definition of a Serious Adverse Event

An adverse event or suspected adverse reaction is considered "serious" if, in the view of either the investigator or sponsor, it results in any of the following outcomes:

1. Death,
2. Life-threatening adverse events,
3. Inpatient hospitalization or prolongation of existing hospitalization,
4. Persistent or significant incapacity or substantial disruption of the ability to conduct normal life function, or
5. Congenital anomaly or birth defect.

If a serious and unexpected AE occurs for which there is evidence suggesting a causal relationship between the study drug and the event (e.g., death from anaphylaxis), the event must be reported as a serious and unexpected suspected adverse reaction even if it is a component of the study endpoint (e.g., all-cause mortality). In addition, the following variables will be collected for SAEs:

- Date AE met criteria for SAE
- Date investigator became aware of SAE
- Explanation of seriousness of this AE
- Date of hospitalization
- Date of discharge
- Probable cause of death
- Date of death
- Autopsy performed
- Causality assessment in relation to study procedure(s)
- Causality assessment in relation to study drug
- Causality assessment in relation to other medication
- Description of AE

## 12.4 Relationship to Study Drugs

Adverse events and SAEs will be collected from the time of signature of informed consent throughout the treatment period. The investigator will assess the causal relationship (i.e., the relationship to study treatment) between the investigational product and the AEs and answer “yes” or “no” to the question “Do you consider that there is a reasonable possibility that the event may have been caused by the investigational product?” For SAEs, causal relationship will also be assessed.

## 12.5 Recording of Adverse Events

Abnormal and clinically significant lab values will be reported as AEs if they fulfill any of the SAE criteria or are the reason for discontinuation of treatment with the study drug. The principal investigator and the study biostatistician will establish the rules for what will constitute abnormal and clinically significant lab values based on established site-specific lab normal ranges. Adverse events, including abnormal lab values (clinically significant and clinically non-significant), will be reviewed monthly for trends by the principal investigator and the medical monitor. Should any abnormal lab values exceed acceptable rates, the FDA will be notified within regulatory timelines. Wherever possible, the reporting investigator will use the clinical, rather than the laboratory term (e.g., anemia versus low hemoglobin value).

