## 8.2 Design

Randomized, prospective, double-blind, placebo-controlled trial of RLF-100 + maximal SOC vs. Placebo + maximal SOC therapy in patients with Critical COVID-19.

Following informed consent, patients will be randomized and administered either placebo or escalating doses of RLF-100 from 50 pmol/kg/hour IV to 150 pmol/kg/hour as three (3) 12 hour infusions each at the same time of day on subsequent study days 1, 2, and 3. Vital signs and telemetry will be monitored throughout the infusion and for 48 hours after completion of all 3 infusions. Pulmonary, cardiovascular, hepatic, CNS, renal, and coagulation functions will be assessed daily for 5 days, and plasma levels of aviptadil and selected cytokines will be measured.

The primary efficacy outcome is a pre-defined cumulative distribution of the time to respiratory failure resolution during the 28-day follow-up with concurrent survival. In other words, recovery from respiratory failure in the absence of survival to the end of the observation period is not considered treatment success. The cumulative distribution over the 28-day interval is consistent with the recent remdesivir approval. However, because the patients enrolled in this trial are exclusively those in category 6 and 7 of the remdesivir trial (where efficacy was not shown at 28 days), we will evaluate their key secondary efficacy endpoint (the percent achieving a NIAID Score 6-8 by Day 28/exit and by Day 60/exit).

Secondary outcome measures will include the cumulative distribution lifetable through Day 28 with attention paid to the Day 28 estimate from the lifetable. Time to ICU discharge, time on invasive mechanical ventilation, time on non-invasive ventilation, and time to discharge alive will be evaluated through Day 28. NIAID area under the curve (AUC) will be evaluated through Day 28.

Other outcome measures to be evaluated through Day 28 include the blood PaO2/FiO2 ratio (enrollment through extubation), oxygenation index, improvement in chest x-ray, IL-6, TNF $\alpha$  and other inflammatory markers.

[figure not shown]
The endpoint rationale is to include the traditional 28-day all-cause mortality plus clinically meaningful

endpoints indicative of multi-dimensional recovery.

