## 12.6 Reporting of Adverse Events

All relevant AEs and special reporting situations, whether serious or non-serious, will be reported from the time a signed and dated Informed Consent Form (ICF) is obtained until completion of the subject’s last study-related procedure. All events that meet the definition of a SAE will be reported as SAEs, regardless of whether they are protocol-specific assessments. All AEs, regardless of seriousness, severity, or presumed relationship to study drug, must be recorded using medical terminology in the source document and the eCRF. Whenever possible, diagnoses will be given when signs and symptoms are due to a common etiology. The sponsor assumes responsibility for appropriate reporting of AEs to the regulatory authorities.

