## **15.13            Overall Safety Endpoints**

Standard safety analyses are planned. Adverse events will be coded in MedDRA. The incidence, severity, relationship, and worst degree will be assessed with attention paid to AEs occurring during the first three days when infusion is to be administered. The incidence of SAEs and deaths/withdrawals due to treatment will also be assessed. The following additional adverse events are of special interest:

- Diarrhea that leads to treatment discontinuation
- Renal failure
- Bleeding events
- Liver toxicity
- Hypotension/shock.

All safety results will be presented separately for each treatment group. Safety endpoints will include adverse events, vital signs (VS), and relevant clinical chemistries and hematology parameters. Safety and tolerability will be assessed using two-sided Fisher Exact tests to compare RLF-100 vs. Placebo. For each treatment group as well as for the difference, two-sided 95% confidence intervals will be computed for each system organ class and for any preferred terms with >10% incidence for either study treatment.

Mean changes from randomization baseline will be displayed for each serum chemistry and hematology parameter as well as the shift; unpaired t-tests will be used to compare RLF -100 vs. Placebo at designated study times. In addition, paired t-tests will be performed for the change from randomization baseline within each study treatment group.

The safety population will be used for these analyses.

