## 21. APPENDIX A; SCHEDULE OF EVENTS

Schedule of Events: Appendix A		Day 1		Day 2		Day 3		Day 4	Day 5	Day 6	Day 7	Day 8- Day 27	Day 28		Day 60
Procedures	Screening	1st Dose a	During infusion	2nd Dose a	During infusion	3rd Dose a	During infusion	Follow- Up	Follow- Up	Follow- Up	Follow- Up	Follow- Up	Follow-Up D28 or day of discharge	Day 28 Follow- up Phone Call	Day 60 Follow- up Phone Call
Informed Consent Process	X														
Evaluation of Exclusion & Inclusion Criteria	X														
Medical History/Demographics	X														
Confirm Eligibility and Randomization		X													
Vital Signs (Pulse, Respirations) b	X	X	X b	X	X b	X	X b								
Blood Pressure c	X	X		X		X									
Weight	X	X		X		X		X	X	X	X		X		
CNS Assessment	X	X		X		X		X	X	X	X		X		
Urine Output and Fluid Intake		X		X		X		X	X	X	X				
IV Administration of Study Drug		X	X	X	X	X	X								
ICU Telemetry: ECG		X		X		X		X	X						
PaO 2 /FiO 2 Ratio	X	X		X		X		X	X	X	X		X		
CBC (Complete Blood Count with Differential & Platelets)	X	X		X		X		X	X	X	X		X		
CMP (Complete Metabolic Panel)	X	X		X		X		X	X	X	X		X		
ABG - Non-ventilated subjects (for PaO 2 /FiO 2 ratio): pH, pCO 2 , pO 2 , CO 2 , HCO 3 per ICU protocol	X								X			X g			

Schedule of Events: Appendix A		Day 1		Day 2		Day 3		Day 4	Day 5	Day 6	Day 7	Day 8- Day 27	Day 28		Day 60
Procedures	Screening	1st Dose a	During infusion	2nd Dose a	During infusion	3rd Dose a	During infusion	Follow- Up	Follow- Up	Follow- Up	Follow- Up	Follow- Up	Follow-Up D28 or day of discharge	Day 28 Follow- up Phone Call	Day 60 Follow- up Phone Call
ABG - Ventilated subjects (for PaO 2 /FiO 2 ratio): pH, pCO 2 , pO 2 , CO 2 , HCO 3 per ICU protocol h	X	X	X	X	X	X	X	X	X	X	X	X	X		
Murray Score	X	X		X		X		X	X	X	X		X		
D-Dimer	X	X		X		X		X	X	X	X		X		
PT/INR/aPTT	X														
Lactic Acid	X	X		X		X		X	X	X	X		X		
Serum/Urine Pregnancy Test (Either Serum or Urine, not both)	X														
HIV (based on history, no HIV testing is required)	X														
Cytokines: Circulating IL6 e,j		X	X e	X	X e	X	X e		X		X		X		
Cytokines: TNFa e,j		X	X e	X	X e	X	X e		X		X		X		

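### Section 12.5 conflicts with 12.2 and 12.6 on when a laboratory abnormality is an adverse event, so non-serious liver and kidney events may be undercounted in the 15.13 special-interest comparisons

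*Combined protocol and SAP*

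**What the plan says.** Section 12.5 sets the rule for laboratory values: "Abnormal and clinically significant lab values will be reported as AEs if they fulfill any of the SAE criteria or are the reason for discontinuation" (here, stopping study drug). The same section leaves the definition of abnormal and clinically significant to be set later, from each site's normal ranges. It also asks investigators to report a clinical term in preference to a laboratory term.

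Two neighbouring sections are broader. Section 12.2 includes in the AE definition "any unfavorable and unintended sign (including an abnormal finding". Section 12.6 says: "All AEs, regardless of seriousness, severity, or presumed relationship to study drug, must be recorded".

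Section 8.2 fixes dosing as "three (3) 12 hour infusions each at the same time of day on subsequent study days 1, 2, and 3". Appendix A schedules the metabolic panel at screening, on Days 1 to 7, and at Day 28 or day of discharge. It schedules urine output on Days 1 to 7.

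Section 15.13 names five special-interest items. Among them are renal failure and "Liver toxicity", neither with a laboratory threshold, and "Diarrhea that leads to treatment discontinuation". It compares arms by two-sided Fisher tests and displays mean changes and shifts for each chemistry and hematology parameter.

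**The concern.** Section 12.5 names two routes by which a clinically significant laboratory value becomes an AE: it is serious, or it is why study drug was stopped. With three daily infusions, the second route closes early. A marked but non-serious rise in creatinine or liver enzymes on Day 5 meets neither condition. Under 12.2 and 12.6 the same finding can be an AE and would then be recorded.

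Renal failure and liver toxicity are often first seen in the laboratory results, and 15.13 gives no definition that would pick them up independently of what the investigator reported. If sites resolve the conflict differently, the special-interest counts depend partly on which section each site followed. If most follow 12.5, the counts are low in both arms and the comparison is less able to show a difference in non-serious liver or kidney harm.

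**Working it through.** The documents give no rate of laboratory abnormalities and no power for safety, so there is no plan figure to reproduce. The check is a count from the schedule and a side-by-side reading.

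**1. Scheduled panels after dosing.** Inputs: dosing on Days 1, 2 and 3 (8.2); metabolic panels after screening on Days 1 to 7 and at Day 28 or discharge (Appendix A).

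- Panels after screening: 7 + 1 = 8.
- Panels after the last dosing day (Days 4, 5, 6, 7 and 28/discharge): 4 + 1 = 5.
- Share: 5/8 = 62.5%. If the Day 1 sample is drawn before the first infusion (an assumption), it belongs to baseline and the share is 5/7 = 71%.
- Study days on which stopping study drug can no longer make a laboratory value an AE: Days 4 to 28, which is 25 of 28 = 89%.

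These are shares of scheduled panels and of days. They are not shares of events.

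**2. The same laboratory finding under each rule.** Take a value already judged clinically significant that the investigator regards as an untoward occurrence.

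| Case | 12.5 read literally | 12.2 with 12.6 |
|---|---|---|
| Any day, serious | AE | AE |
| Days 1–3, non-serious, study drug stopped because of it | AE | AE |
| Days 1–3, non-serious, study drug continued | not an AE | AE |
| Day 4 onward, non-serious | not an AE | AE |

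The sections disagree in the last two rows. During dosing a non-serious value still has one route in. From Day 4 it has none.

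**3. Effect on 15.13.** A finding that is not recorded as an AE cannot be coded, so it cannot enter the Fisher comparison of AEs or the special-interest counts. Since 15.13 gives no laboratory definition of renal failure or liver toxicity, nothing in that section restores the missing events to those counts.

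**4. Size.** The undercount lies between two limits. It is zero if sites follow 12.2 and 12.6 and report clinical diagnoses. If sites follow 12.5 literally, it is every non-serious, laboratory-only liver or kidney abnormality that did not stop study drug, which from Day 4 means all of them. The documents give nothing that places the trial between these limits.

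**The case against.** The other side has several good points.

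- **The wording is permissive.** Section 12.5 says if, not only if, and later refers to adverse events as including abnormal laboratory values. Read with 12.2 and 12.6, it need not exclude anything. This stands as a possible reading. However, naming two conditions for values already judged clinically significant serves little purpose unless it limits reporting, and a site could reasonably apply it that way.
- **Clinical diagnoses get through.** Once renal failure or liver toxicity is diagnosed, it is reportable under its clinical name whether or not it is serious. This stands, but it does not help an abnormality that nobody labels.
- **The SAE route is wide.** A longer hospital stay or a threat to life qualifies, so much renal failure in the ICU would count as serious. This also stands. The gap concerns non-serious events.
- **Other analyses see the data.** The 15.13 shifts use every chemistry value, and a conventional shift table counts patients. Section 15.8 counts days free of organ failure, with liver and kidney among the organs. Section 12.5 adds a monthly review of abnormal values, significant or not. These are real but partial offsets. Shifts are by parameter, 15.8 pools several organs into one measure, and the monthly review is for trends, so none yields a count of patients with renal failure or with liver toxicity.

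Three stronger readings are tempting, and the documents do not support them.

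- A reader might infer that these events *are* undercounted. The documents show a conflict between rules, not how sites resolved it.
- A reader might infer a biased comparison, or quote a loss of power. The rule applies equally to both arms under blinding. Any power figure would need event rates and capture fractions that the documents do not give, and serious events pass the 12.5 rule in any case.
- A reader might infer that 12.5 also suppresses diarrhea, because 11.5 says of watery diarrhea that "the infusion rate should be first reduced by 50% to relieve symptoms" before any stop. Diarrhea is not a laboratory value, so 12.5 does not govern it. Its restriction comes only from the special-interest line in 15.13. Other diarrhea remains an ordinary AE under 12.6, is coded, and is compared between arms.

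**Conclusion.** The point holds as an inconsistency with a possible cost. Sections 12.5, 12.2 and 12.6 give different answers for non-serious laboratory abnormalities. From Day 4, when 5 of the 8 scheduled on-study panels fall, 12.5 leaves only the SAE route. Non-serious liver and kidney events may therefore be undercounted, or recorded differently from site to site, in the 15.13 special-interest comparisons. The consequence is lower sensitivity in both arms. No directional bias is shown, and the amount lost cannot be computed.

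This rests on two assumptions: that at least some sites would read 12.5 as a restriction, and that AEs are collected until the last study procedure, as 12.6 says. Section 12.4 refers only to the treatment period, so the collection window also needs to be made consistent. The change is worth making because it is cheap and uses data already planned, not because a loss has been demonstrated.

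**What to change.** 1. Reconcile 12.5 with 12.2 and 12.6, so that one rule states when a clinically significant laboratory value is recorded as an AE and that rule does not depend on seriousness or on stopping study drug.
2. In 15.13, and in the SAP that 14.1 says will be finalized before database lock, define the renal-failure and liver-toxicity special-interest events by thresholds fixed before unblinding. Apply them by program to the metabolic-panel and urine-output data already scheduled in Appendix A, independently of investigator AE reporting. Show these counts beside the investigator-reported ones.
3. Optional and minor: tabulate all diarrhea from the first infusion, with infusion slowing and discontinuation as subsets. This adds a table and changes nothing in patient management.

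The cost is protocol and SAP wording, one programmed derivation, and some additional AE entries per patient. No new samples or visits are needed.

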## 12.6 Reporting of Adverse Events

All relevant AEs and special reporting situations, whether serious or non-serious, will be reported from the time a signed and dated Informed Consent Form (ICF) is obtained until completion of the subject’s last study-related procedure. All events that meet the definition of a SAE will be reported as SAEs, regardless of whether they are protocol-specific assessments. All AEs, regardless of seriousness, severity, or presumed relationship to study drug, must be recorded using medical terminology in the source document and the eCRF. Whenever possible, diagnoses will be given when signs and symptoms are due to a common etiology. The sponsor assumes responsibility for appropriate reporting of AEs to the regulatory authorities.

## 12.7 Reporting of Serious Adverse Events

Reportable SAEs will be sent to the IRB and FDA by the sponsor. When a SAE is discovered, it will be reported immediately (within 24 business hours) to the Medical Monitor. Serious adverse events will be reported within 24 business hours of the site’s knowledge of the event to the Sponsor, Medical Monitor, and study site investigators.

